with HVPG cutoff levels of 10 and 12 mmHg. The optimal operating point (OOP) will be determined as the point closest to '0,1' on the ROC curve (representing 100% sensitivity and 100% specificity). All clinical variables (e.g., concomitant imaging results, presence of cancer or ascites, blood tests, fibrosis and MELD scores etc.) will also be compared to the SHAPE values. When both types of variables are ordinal or continuous, correlations will be calculated. When one type of variable is nominal and one continuous non-parametric rank order tests such as Mann-Whitney U-tests or Kruskal-Wallis tests will be performed [Rosner 1990]. All of the statistical analyses proposed for the human clinical trial will be repeated split by racial and ethnic groups to determine if clinically important race/ethnicity differences exist in the ability of SHAPE to diagnose portal hypertension.

All analyses and computations will be performed using NCSS/PASS 2008 and Stata 12.0 (Stata Corporation, College Station, TX), while the study database will be designed and implemented in Filemaker Pro 10.0 (Filemaker Inc, Santa Clara, CA). This database will contain all patient information (except names and other identifiers), including results of biopsies, HVPG and SHAPE measurements as well as the clinical variables.

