### 7.2 Statistical Analyses

#### 7.2.1 Hypotheses

$H_1$ : Can patients with HVPG of 10 mmHg or greater be identified using SHAPE? The fundamental hypothesis is that a sensitivity of 89% and a specificity of 81 % can be achieved by using SHAPE measurements to identify patients with HVPGs of 10 mmHg or greater.

H2: A correlation coefficient of 0.82 will be achieved between in vivo SHAPE and HVPG measurements.

H3: A correlation coefficients above 0.90 will be achieved between SHAPE and repeat HVPG results.

H4: SHAPE will significantly differentiate responders from non-responders using clinical outcomes as the reference standard.

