### 7.2.2 Analysis of Results

The findings of SHAPE will be correlated to the invasive catheter based measurements of portal vein blood pressure (i.e., HVPG) using least squares, multiple linear regression analysis with robust standard errors. Receiver operating characteristic (ROC) curves will be computed using a continuous scale with HVPG cutoff levels of 10 and 12 mmHg. The optimal operating point (OOP) will be determined as the point closest to '0,1' on the ROC curve (representing 100% sensitivity and 100% specificity). All clinical variables (e.g., concomitant imaging results, presence of cancer or ascites, blood tests, fibrosis and MELD scores etc.) will also be compared to the SHAPE values. When both types of variables are ordinal or continuous, correlations will be calculated. When one type of variable is nominal and one continuous non-parametric rank order tests such as Mann-Whitney U-tests or Kruskal-Wallis tests will be performed [Rosner 1990]. All of the statistical analyses proposed for the human clinical trial will be repeated split by racial and ethnic groups to determine if clinically important race/ethnicity differences exist in the ability of SHAPE to diagnose portal hypertension.

All analyses and computations will be performed using NCSS/PASS 2008 and Stata 12.0 (Stata Corporation, College Station, TX), while the study database will be designed and implemented in Filemaker Pro 10.0 (Filemaker Inc, Santa Clara, CA). This database will contain all patient information (except names and other identifiers), including results of biopsies, HVPG and SHAPE measurements as well as the clinical variables.

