### 7.2.3 Sample Size Calculation

As the most clinically important aim, the sample size analysis is based on specific aim 1 where each patient represents an independent entity. Based on our pilot study, the sensitivity and specificity of

SHAPE for the diagnosis of portal hypertension (i.e., HVPG > 10 mmHg) is 89% and 88%, respectively [Eisenbrey et al. 2013]. However, the confidence intervals achieved in the pilot study were (due to the limited sample size) very wide (worst case scenario: 52–100%). Hence, a power analysis was performed using NCSS/PASS 2008 (NCSS, East Kaysville, UT) to estimate the number of cases required to produce clinically acceptable 95% two-sided confidence intervals (for one correlation) [Newcombe 1998]. Table 2 below illustrates sample size calculations for the number of independent observations needed in the study population based upon 95% two-sided confidence intervals ranging from 0.06 to 0.10 for one correlation. A sample size between 259 and 278 subjects will provide 95% confidence intervals from 0.84 to 0.92 (i.e., a width of 0.08). A similar analysis was conducted based on the correlation between SHAPE and HVPG of 0.82 obtained in our pilot study [Eisenbrey et al. 2012a]. In that case to demonstrate that SHAPE can accurately measure HVPG values with a correlation coefficient of 0.82 requires between 264 and 343 patients (for confidence interval widths of 0.08 and 0.07, respectively). Hence, we selected a sample size for this study of 300 subjects.

Table 2: Sample size calculations for different 95% confidence intervals in the human clinical trial.

Target width	Proportion (R)	Lower limit	Upper limit	Sample size (N)
0.06	0.88	0.848	0.908	483
0.06	0.89	0.857	0.917	450
0.07	0.88	0.842	0.912	359
0.07	0.89	0.851	0.921	335
0.08	0.88	0.836	0.916	278
0.08	0.89	0.845	0.925	259
0.09	0.88	0.830	0.920	222
0.09	0.89	0.839	0.929	207
0.10	0.88	0.824	0.923	181
0.10	0.89	0.833	0.933	170

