The Interventional Radiology Divisions at Thomas Jefferson University (TJU) and the Hospital of the University of Pennsylvania (HUP) performs approximately 85 and 100 transjugular liver biopsy procedures with pressure measurements per year, respectively. The patient population of this project will reflect the population demographics found at major American urban academic health centers. The overall hospital demographics for TJU and HUP include 66% Caucasian, 30% African American, and 4% Asian, with 10% representing Hispanic patients. The goal is to enroll 300 patients over the last 3 years of this project, which means we are aiming for a recruitment rate of approximately 54%.

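### The race and ethnicity analysis aims to find differences between groups but only repeats each analysis within groups, with no between-group contrast and, read literally, a separate SHAPE cut-off per group

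*Combined protocol and SAP*

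**What the plan says.** Section 7.2.2 (Analysis of Results) states that every analysis "will be repeated split by racial and ethnic groups to determine if clinically important race/ethnicity differences exist" in the diagnostic ability of SHAPE. The Synopsis, under Statistical Methodology, has the same plan.

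The analyses to be repeated include the regression of SHAPE against HVPG, the ROC curves at HVPG cut-offs of 10 and 12 mmHg, and the choice of operating point as the ROC point nearest to perfect sensitivity and specificity. The regression has no stated race or ethnicity term. No size is given for a clinically important difference.

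Section 7.2.3 sets the total: "Hence, we selected a sample size for this study of 300 subjects". It expects that "The patient population of this project will reflect the population demographics found at major American urban academic health centers" and gives the overall mix at the two hospitals as "66% Caucasian, 30% African American, and 4% Asian, with 10% representing Hispanic patients". The sample size rests on precision in the whole cohort, not in any subgroup.

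The Synopsis and Section 6.4 mention an unpaired t-test for comparing sensitivities, specificities and accuracies, but do not say what is compared with what. Section 7.2.2 does not mention this test.

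**The concern.** There are two separate problems.

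- **No contrast.** Asking whether groups differ requires an estimate of the difference and its uncertainty. Separate results per group do not supply that until someone chooses how to compare them. Under this plan the choice would be made after the data are seen.
- **Moving cut-off.** If the operating point is chosen again in each group, a difference in sensitivity or specificity mixes three things: a real difference, a different threshold, and optimism from picking the best point on that group's own curve. Optimism grows as the group shrinks, so a small group will tend to look better for no biological reason. This affects sensitivity, specificity and accuracy. It does not affect the AUC or the correlation, which use no cut-off.

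At stake is a false statement that a diagnostic test works better or worse in one racial or ethnic group, or a real difference reported without a usable estimate of its size.

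**Working it through.** **1. The plan's own figures.** Section 7.2.3 can be reproduced.

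- Exact (Clopper-Pearson) 95% intervals of width 0.08 need 278 patients at a proportion of 0.88 and 259 at 0.89, as in Table 2.
- For r = 0.82, Fisher's z is atanh(0.82) = 1.157. With n = 264 the half-width is 1.96/√261 = 0.121, which gives 0.776 to 0.856, a width of 0.08 as stated.

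Both calculations concern the whole cohort.

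**2. Expected group sizes** (share × 300, Section 7.2.3). Caucasian 0.66 × 300 = 198; African American 0.30 × 300 = 90; Asian 0.04 × 300 = 12; Hispanic 0.10 × 300 = 30, against 270 non-Hispanic. The three racial shares add to 100%, so Hispanic ethnicity overlaps them. These are expectations from overall hospital demographics, not quotas.

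**3. Within-group precision for r = 0.82** (95% CI = tanh(1.157 ± 1.96/√(n − 3))).

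| n | 95% CI |
|---|---|
| 198 | 0.77–0.86 |
| 90 | 0.74–0.88 |
| 30 | 0.65–0.91 |
| 12 | 0.46–0.95 |

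For sensitivity, the documents do not give the prevalence of HVPG of 10 mmHg or more, so I assume 30–70%. About 4 to 8 of 12 patients would then be diseased. An observed 4 of 5 has an exact 95% CI of 28–99%.

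**4. Optimism from a separate cut-off per group.** Section 7.2.1 hypothesises "a sensitivity of 89% and a specificity of 81 % can be achieved by using SHAPE measurements". I took normal SHAPE scores with equal variance. The separation is z(0.89) + z(0.81) = 1.227 + 0.878 = 2.104 standard deviations, identical in every group. By symmetry the true nearest-to-perfect point has sensitivity and specificity both equal to Φ(2.104/2) = 0.854, a sum of 1.707. I simulated each group size, chose the operating point from that group's own ROC curve, and compared the apparent sum with 1.707. Diseased counts were fixed at prevalence × n.

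| n | Mean inflation of sensitivity + specificity, prevalence 30–70% |
|---|---|
| 198 | about 3 points |
| 90 | 4–5 points |
| 12 | 13–14 points |

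If the number diseased is left to vary at random, the last row becomes about 13–15. Following the plan literally would therefore favour the 12-patient group over the 198-patient group by about 10 points in this sum, with no true difference.

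**5. Chance gaps even at a common cut-off.** If true sensitivity is 0.89 everywhere, an observed gap of 10 points or more arises by chance in 4–17% of trials for African American against Caucasian, 17–37% for Hispanic against non-Hispanic, and 47–72% for Asian against Caucasian (prevalence 70% down to 30%).

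**6. What a direct contrast could detect** (two-sided 5%). For sensitivity 0.89 against 0.69, power = Φ[(0.20 − 1.96·s₀)/s₁], with s₀ the pooled and s₁ the unpooled standard error. Example at 50% prevalence, 99 against 45 diseased: pooled proportion 0.8275, s₀ = 0.0679, s₁ = 0.0758, power = Φ(0.88) = 81%. For correlations 0.82 against 0.62, power = Φ[0.432/√(1/(n₁−3) + 1/(n₂−3)) − 1.96].

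| Contrast | Sensitivity, prevalence 30 / 50 / 70% | Correlation |
|---|---|---|
| 198 vs 90 | 61 / 81 / 91% | 92% |
| 270 vs 30 | 42 / 57 / 68% | 57% |
| 198 vs 12 | 28 / 36 / 43% | 24% |

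The normal approximation is rough in the last row.

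**The case against.** A reader might infer that the split analysis cannot show any difference. The documents do not support that. The racial groups are disjoint, so their separate estimates and intervals can be contrasted afterwards. For 198 against 90 patients, a 20-point gap in sensitivity or a fall in correlation from 0.82 to 0.62 would probably be seen (step 6). This stands, although such a contrast would be chosen after the data are known.

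A reader might also infer that groups will be compared by eye. The plan does not say so; it is silent on how the split results are to be compared. The unpaired t-test in the Synopsis and Section 6.4 could conceivably be meant for racial groups, since it needs independent samples. But it names no comparator, is absent from Section 7.2.2, and is not tied to race or ethnicity anywhere, so it does not fill the gap.

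The separate cut-off is the literal reading of repeating all analyses. Nothing rules out also reporting accuracy at the overall cut-off, but nothing provides for it either.

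Nor is the absence of an interaction test what defeats the smallest group. With about 12 patients, a direct test has only 28–43% power for a 20-point gap in sensitivity, and the correlation would have to fall from 0.82 to about 0.20 for 80% power.

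Finally, race and ethnicity appear in neither the objectives nor the hypotheses, and the sample size was not set for them. That limits the weight of the point.

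**Conclusion.** The concern holds as a mismatch between aim and method. The plan sets out to determine whether differences exist, specifies only within-group repeats, and names no contrast. Taken literally, it compares accuracies at group-specific cut-offs whose optimism runs from about 3 points in sensitivity plus specificity at n = 198 to 13–14 at n = 12, which manufactures differences that depend on group size.

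These sizes rest on equal-variance normal scores, the hypothesised 89% and 81%, an assumed prevalence of 30–70%, and recruitment that follows the hospital mix. The direction does not depend on the exact values: optimism from selecting a cut-off shrinks as the sample grows.

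The finding does not extend to saying that large differences between the two biggest groups would be missed, or that a better method would make a group of about 12 informative. It concerns a secondary analysis and leaves the main accuracy and correlation results untouched. It should be corrected, because the correction uses the same data.

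**What to change.** Amend Section 7.2.2 and the matching Synopsis text as follows.

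- Apply the single SHAPE cut-off derived from the whole cohort in every racial and ethnic group.
- Report between-group differences in sensitivity, specificity, AUC and correlation, each with a 95% CI. State beforehand what size of difference would count as clinically important, so that the intervals can be read against it.
- Support these with SHAPE-by-race and SHAPE-by-ethnicity interaction terms in the HVPG regression. A slope interaction is not itself a difference in accuracy or correlation, so the intervals should lead.
- Show groups with fewer than about 20 patients descriptively only.
- Say what the unpaired t-test in the Synopsis and Section 6.4 compares.

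The cost is wording: no added patients, visits or measurements, and within-group estimates can still be shown. There is a small downside. Power is limited, above all outside the two largest groups, so a non-significant interaction could be misread as equivalence. The plan should state that it will not be reported as evidence of no difference and that conclusions rest on the confidence intervals.

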### 7.2.3 Sample Size Calculation

As the most clinically important aim, the sample size analysis is based on specific aim 1 where each patient represents an independent entity. Based on our pilot study, the sensitivity and specificity of

SHAPE for the diagnosis of portal hypertension (i.e., HVPG > 10 mmHg) is 89% and 88%, respectively [Eisenbrey et al. 2013]. However, the confidence intervals achieved in the pilot study were (due to the limited sample size) very wide (worst case scenario: 52–100%). Hence, a power analysis was performed using NCSS/PASS 2008 (NCSS, East Kaysville, UT) to estimate the number of cases required to produce clinically acceptable 95% two-sided confidence intervals (for one correlation) [Newcombe 1998]. Table 2 below illustrates sample size calculations for the number of independent observations needed in the study population based upon 95% two-sided confidence intervals ranging from 0.06 to 0.10 for one correlation. A sample size between 259 and 278 subjects will provide 95% confidence intervals from 0.84 to 0.92 (i.e., a width of 0.08). A similar analysis was conducted based on the correlation between SHAPE and HVPG of 0.82 obtained in our pilot study [Eisenbrey et al. 2012a]. In that case to demonstrate that SHAPE can accurately measure HVPG values with a correlation coefficient of 0.82 requires between 264 and 343 patients (for confidence interval widths of 0.08 and 0.07, respectively). Hence, we selected a sample size for this study of 300 subjects.

Table 2: Sample size calculations for different 95% confidence intervals in the human clinical trial.

Target width	Proportion (R)	Lower limit	Upper limit	Sample size (N)
0.06	0.88	0.848	0.908	483
0.06	0.89	0.857	0.917	450
0.07	0.88	0.842	0.912	359
0.07	0.89	0.851	0.921	335
0.08	0.88	0.836	0.916	278
0.08	0.89	0.845	0.925	259
0.09	0.88	0.830	0.920	222
0.09	0.89	0.839	0.929	207
0.10	0.88	0.824	0.923	181
0.10	0.89	0.833	0.933	170

The Interventional Radiology Divisions at Thomas Jefferson University (TJU) and the Hospital of the University of Pennsylvania (HUP) performs approximately 85 and 100 transjugular liver biopsy procedures with pressure measurements per year, respectively. The patient population of this project will reflect the population demographics found at major American urban academic health centers. The overall hospital demographics for TJU and HUP include 66% Caucasian, 30% African American, and 4% Asian, with 10% representing Hispanic patients. The goal is to enroll 300 patients over the last 3 years of this project, which means we are aiming for a recruitment rate of approximately 54%.

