direct supervision of a medical doctor. Additionally, resuscitation equipment will be in immediate proximity to the patient during Sonazoid infusion. Three vials (6 ml) of Sonazoid microbubbles (16  $\mu$ l per vial when reconstituted) will be prepared for each subject by resuspending each vial in 2 ml of water for injection, supplied by GEHC, as described in the instructions provided by GEHC (Appendix B). Infusions will be performed as described in Appendix B. All materials and supplies used for the infusion procedure will be identical to those described in GE Healthcare's current Sonazoid IND. Briefly, anintravenous cannula will be placed in a vein in the subject's arm. A 0.9% NaCl solution will be started and used to fill up the connecting tubes before being connected to a 3-way stopcock. The stopcock will then be connected to the extension tubing leading to the cannula. All three vials of suspended Sonazoid will be drawn into a 10 ml syringe, placed in a syringe pump at the same level or below the patient, and connected directly to the stopcock. After the stopcock to the 0.9% NaCl solution has been opened, the saline solution will be infused at a rate of at least 2 ml/min. Then, Sonazoid will be co-infused at the target rate of 0.024  $\mu$ l/kg body weight/minute (suspension infusion rate of 0.18 ml/kg/hour), but the rate may be reduced if necessary to achieve optimal levels of contrast. This infusion rate was selected based on our group's previous experiences with Sonazoid infusion in human subjects in general [Halpern et al. 2002; Landmark et al. 2008] and in SHAPE portal hypertension subjects in particular [Eisenbrey et al. 2013]. This dosing scheme is designed to avoid (or limit) the number of cases that has to be discarded due to insignificant enhancement in the hepatic veins (as in our pilot study; Eisenbrey et al. 2013). The dosage is based off the GEHC provided, study specific resuspension and infusion instructions (Appendix B) and the total Sonazoid dose given over a maximum of 15 minutes (0.36  $\mu$ l/kg) will be well below the maximal tested dose which was still found safe in Phase I clinical trials (2.7  $\mu$ l of microbubbles/kg in PBI 0001 as detailed in the Sonazoid Investigator's Brochure). The duration of contrast agent infusion will range from 5 to 10 minutes.

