**Statistical Methodology:** This project is a large clinical trial to further develop SHAPE and to employ this method to conduct a large scale human clinical trial to conclusively establish the accuracy of SHAPE for the assessment of portal hypertension. Our statistical analysis will address following major questions:

1. Can patients with HVPG of 10 mmHg or greater be identified using SHAPE? The fundamental hypothesis is that a sensitivity of 89% and a specificity of 81 % can be achieved by using SHAPE measurements to identify patients with HVPGs of 10 mmHg or greater.
2. Can portal vein pressures (in the form of HVPGs) in patients with liver disease be quantified accurately using SHAPE? The fundamental hypothesis is that a correlation coefficient of 0.82 can be achieved between *in vivo* SHAPE and HVPG measurements.
3. Can SHAPE accurately monitor disease progression or treatment response in patients identified with portal hypertension? The fundamental hypothesis is that correlation coefficients above 0.90 can be achieved between SHAPE and repeat HVPG results and that SHAPE will significantly differentiate responders from non-responders (using clinical outcomes as the reference standard).

The findings of SHAPE will be correlated to the invasive catheter based measurements of portal vein blood pressure (i.e., HVPG) using least squares, multiple linear regression analysis with robust standard errors. Comparisons of sensitivities, specificities and accuracies for diagnosing portal hypertension with SHAPE will be conducted with an unpaired Student's t-test (using HVPG measurements as the reference standard). Receiver operating characteristic (ROC) curves will be computed using a continuous scale

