#### 4. TRIAL POPULATION

Trial Population: This trial will consist of up to 300 adults (21 years of age or older) undergoing trans-jugular liver biopsy with HVPG measurement at TJU or at HUP.

Subjects eligible for trial enrollment will be identified by the co-investigators, [name] (at TJU) and [name] (at HUP) from their patient population of subjects scheduled for a trans-jugular liver biopsy. The research coordinators for this study will explain the study to the patients at the respective clinical sites. The patient will be given time to consider the risks and benefits of the study and ask questions about participation. The coordinator will review the consent form with the patient and then the patient will be given the form to review. The patient, coordinator, and a study investigator will all sign the consent form. The patient will be given a copy of the signed consent form for their records.

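### The 0.08 confidence interval width for sensitivity and specificity needs at least 537 patients, not 259 to 278, and no split of 300 delivers it; H1's specificity (81%) is also not the one planned on (88%)

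*Combined protocol and SAP*

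**What the plan says.** Section 7.2.3 says the calculation rests on specific aim 1, described there as the most important clinically. It takes from the pilot study that the sensitivity and specificity of "SHAPE for the diagnosis of portal hypertension (i.e., HVPG > 10 mmHg) is 89% and 88%, respectively", notes that the pilot intervals were very wide, and introduces Table 2 as the number of independent observations needed, "based upon 95% two-sided confidence intervals ranging from 0.06 to 0.10 for one correlation". It then draws the conclusion: "A sample size between 259 and 278 subjects will provide 95% confidence intervals from 0.84 to 0.92 (i.e., a width of 0.08"). A second calculation, for a SHAPE–HVPG correlation of 0.82, gives 264 patients (width 0.08) and 343 patients (width 0.07). The section ends: "Hence, we selected a sample size for this study of 300 subjects".

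H1 in Section 7.2.1 postulates "a sensitivity of 89% and a specificity of 81 % can be achieved by using SHAPE measurements", and the Synopsis repeats the same two values. Table 2 has rows for 0.88 and 0.89 only.

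Section 4 describes enrolment without any quota by HVPG status: "This trial will consist of up to 300 adults". No section states the expected proportion with HVPG of 10 mmHg or more.

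**The concern.** Sensitivity is estimated only in patients who have the condition, and specificity only in those who do not. A one-proportion sample size computed for each is therefore a count within that subgroup, and the two counts add. Section 7.2.3 instead treats 259 to 278 as total enrolment and sets 300 against it.

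That sentence is the plan's only precision statement for the aim said to drive the sample size. If N is misread, anyone judging whether the trial can establish diagnostic accuracy is given a precision that the design cannot produce. The move from 88% in the calculation to 81% in H1 adds to the problem, because at a fixed n a proportion nearer to 0.5 has a wider interval.

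**Working it through.** **Inputs.** From Section 7.2.3: two-sided 95% intervals, proportions 0.89 and 0.88, target width 0.08, Table 2, r = 0.82, total N = 300. From Section 7.2.1: sensitivity 0.89, specificity 0.81, cut-off HVPG of 10 mmHg or more. Prevalence is not given and is varied below as an assumption.

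**Step 1: reproduce Table 2.** Exact (Clopper-Pearson) limits with x = pn:

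- lower = Beta quantile (0.025; x, n − x + 1)
- upper = Beta quantile (0.975; x + 1, n − x)

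The smallest n with upper − lower ≤ target equals the tabulated N in all ten rows. For example:

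- p = 0.88, n = 278: 0.836 to 0.916
- p = 0.89, n = 259: 0.845 to 0.925

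The sentence's 0.84 to 0.92 is the 0.88 row, rounded.

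**Step 2: is it a correlation calculation?** Fisher z limits are tanh(atanh r ± 1.96/√(n − 3)). Width 0.08 would need only 129 (r = 0.88) or 111 (r = 0.89), so Table 2 is not a correlation table. The r = 0.82 figures do reproduce this way: width 0.080 at n = 264 and 0.070 at n = 343. At n = 300 the interval is 0.779 to 0.854, width 0.075.

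**Step 3: total needed for both measures.**

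| Width | Sensitivity 0.89: positives | Specificity 0.88: negatives | Minimum total | Specificity 0.81: negatives | Minimum total |
|---|---|---|---|---|---|
| 0.08 | 259 | 278 | 537 | 393 | 652 |
| 0.10 | 170 | 181 | 351 | 255 | 425 |

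These totals are minima, reached only if the case mix matches the split (259/537 = 48% positive for the first). At other prevalences the total is max(259/prevalence, 278/(1 − prevalence)), rounded up: 864 at 30%, 556 at 50%, 927 at 70%. Even the widest row of Table 2 (0.10) needs more than 300.

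**Step 4: what 300 delivers.** Exact widths with 300 × prevalence positives and the rest negative:

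| Assumed prevalence | Positive/negative | Sensitivity 0.89 | Specificity 0.88 | Specificity 0.81 |
|---|---|---|---|---|
| 20% | 60/240 | 0.174 | 0.086 | 0.103 |
| 35% | 105/195 | 0.129 | 0.096 | 0.115 |
| 50% | 150/150 | 0.107 | 0.110 | 0.131 |
| 70% | 210/90 | 0.089 | 0.145 | 0.171 |

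Over all splits, the smallest achievable value of the wider interval is 0.108 (145/155) with specificity 0.88, and 0.120 (120/180) with specificity 0.81.

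**Step 5: one measure at a time.**

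- Sensitivity reaches 0.08 only with 259 positives (259/300 = 86.3%). The other 41 give a specificity (0.88) width of 0.220.
- Specificity 0.88 reaches 0.08 only with 278 negatives (at most 22/300 = 7.3% positive). The other 22 give a sensitivity width of 0.298.
- Specificity 0.81 cannot reach 0.08: all 300 patients negative would give 0.092.

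**The case against.** **The sentence names neither measure and speaks of one correlation, which would use every patient.** The sentence indeed does not name them, so the claim is implied rather than stated. But the values are the pilot sensitivity and specificity just cited, the table column is headed as a proportion, and Step 2 rules out a correlation. The wording is a mislabel.

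**The arithmetic is right, and 300 has other support.** Both are true. All ten rows are correct, and the choice of 300 follows directly on the r = 0.82 calculation, which properly counts all patients. No test, power claim or success threshold hangs on 0.08, and the reported intervals will show the real precision. This limits the consequence to the stated precision for aim 1. It does not make that statement correct.

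**A target of 81% below a pilot estimate of 88% is not in itself a contradiction.** This is fair. The documents do not explain the gap, though, and the precision for the value named in H1 is nowhere calculated. The figures at 0.81 show what H1 implies; they are not errors in Table 2.

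**The documents hint at a prevalence.** Section 7.2.3 gives the worst pilot interval as 52–100%. An exact interval for 8 of 9 is 51.8% to 99.7%, which would suggest about 9 positives among the 45 pilot patients (20%), or a higher share if discarded cases reduce the denominator. This is an inference that assumes an exact interval. It supports including 20% in the range; at that level the sensitivity interval is 0.174 wide.

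**Conclusion.** The concern holds. Section 7.2.3 reads the denominator of each measure as total enrolment. A width of 0.08 for both sensitivity 0.89 and specificity 0.88 needs at least 537 patients, or at least 652 with H1's specificity. At 300, the wider interval is at least 0.108 (0.120 with 81%) at any prevalence. That conclusion needs no prevalence assumption; the individual widths in Step 4 do.

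At balanced prevalence the shortfall is moderate, about ±5.5 points (0.110/2) instead of ±4 (0.08/2). It becomes large for the smaller group when prevalence is skewed. All widths assume 300 evaluable patients and are best cases. Enrolment is capped at 300, and the Synopsis says the dosing scheme aims to avoid or limit "the number of cases that has to be discarded due to insignificant enhancement in the hepatic veins", as happened in the pilot, without giving a rate.

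The difference between 81% and 88% is real and unexplained. The sample size of 300 remains supported by the correlation calculation.

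**What to change.** Keep 300 subjects and change the text of Section 7.2.3:

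- Replace the 0.08-width sentence with expected exact widths over a stated prevalence range. For example: with 300 evaluable subjects and an assumed prevalence of HVPG ≥ 10 mmHg of 20%, 35%, 50% or 70%, the 95% interval is expected to be 0.174, 0.129, 0.107 or 0.089 wide for a sensitivity of 89%, and 0.086, 0.096, 0.110 or 0.145 wide for a specificity of 88% (0.103, 0.115, 0.131 or 0.171 for 81%).
- Relabel Table 2 as exact intervals for one proportion. State that N is the number of HVPG-positive patients for sensitivity and HVPG-negative patients for specificity.
- Reconcile 81% with 88%. Preferably use one value in the Synopsis, H1 and the calculation; otherwise explain why the hypothesis and the planning value differ and give the precision for both.
- Present the r = 0.82 calculation as the support for 300 (width 0.075).

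This needs no extra patients, procedures or analyses. The cost is a less favourable stated precision for aim 1.
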